10.0 Adverse Event (AE) Reporting and Monitoring

The site principal investigator is responsible for reporting any/all adverse events to the sponsor as described within the protocol. Refer to the adverse event and serious adverse event sections of the protocol for detailed information.

NOTE: Please see Appendix III for specific AE reporting regarding the study drug olaparib.

The sponsor/sponsor-investigator is responsible for notifying FDA and all participating investigators in a written safety report of any of the following:

- Any suspected adverse reaction that is both serious and unexpected.
- Any findings from laboratory animal or *in vitro* testing that suggest a significant risk for human subjects, including reports of mutagenicity, teratogenicity, or carcinogenicity.
- Any findings from epidemiological studies, pooled analysis of multiple studies, or clinical studies, whether or not conducted under an IND and whether or not conducted by the sponsor, that suggest a significant risk in humans exposed to the drug.
- Any clinically important increase in the rate of a serious suspected adverse reaction over the rate stated in the protocol or Investigator's Brochure (IB).

Definitions

Adverse Event

Any untoward medical occurrence associated with the use of a drug in humans, whether or not considered drug related.

Suspected Adverse Reaction

Any adverse event for which there is a reasonable possibility that the drug caused the adverse event.

Expedited Reporting

Events reported to sponsor within 24 hours, 5 days or 10 days of study team becoming aware of the event.

Routine Reporting

Events reported to sponsor via case report forms

Events of Interest

Events that would not typically be considered to meet the criteria for expedited reporting, but that for a specific protocol are being reported via expedited means in order to facilitate the review of safety data (may be requested by the FDA or the sponsor).

Adverse events after the 30 day follow up period

For Pharmacovigilance purposes and characterization, any SAE of MDS/AML or new primary malignancy occurring after the 30 day follow up period should be reported to AstraZeneca Patient Safety regardless of investigator's assessment of causality or knowledge of the treatment arm. Investigators will be asked during the regular follow up for overall survival if the patient has developed MDS/AML or a new primary malignancy and prompted to report any such cases.

At any time after a patient has completed the study, if an Investigator learns of any SAE including sudden death of unknown cause, and he/she considers there is a reasonable possibility that the event is causally related to the investigational product, the investigator should notify AstraZeneca, Patient Safety.

If patients who are gaining clinical benefit are allowed to continue study treatment post data cut off and/or post study completion, then all SAEs must continue to be collected and reported to Patient Safety within the usual timeframe.

Otherwise, after study treatment completion (i.e. after any scheduled post treatment follow-up period has ended) there is no obligation to actively report information on new AEs or SAEs occurring in former study patients. This includes new AEs/SAEs in patients still being followed up for survival but who have completed the post treatment follow up period (30 days).

Olaparib adverse events of special interest

Adverse events of special interest [AESI] are events of scientific and medical interest specific to the further understanding of olaparib's safety profile and require close monitoring and rapid communication by the investigators to AstraZeneca. Adverse Events of Special Interest for olaparib are the Important Potential Risks of MDS/AML, new primary malignancy (other than MDS/AML) and pneumonitis.

A questionnaire will be sent to any investigator reporting an AESI, as an aid to provide further detailed information on the event. During the study there may be other events identified as AESIs that require the use of a questionnaire to help characterize the event and gain a better understanding regarding the relationship between the event and study treatment.

There is currently no specific treatment in the event of overdose with olaparib and possible symptoms of overdose are not established.

Olaparib must only be used in accordance with the dosing recommendations in this protocol. Any dose or frequency of dosing that exceeds the dosing regimen specified in this protocol should be reported as an overdose. The Maximum Tolerated Dose is 300 mg twice daily (tablet).

Adverse reactions associated with overdose should be treated symptomatically and should be managed appropriately.

An overdose with associated AEs is recorded as the AE diagnosis/symptoms on the relevant AE modules in the CRF.

If an overdose on an AstraZeneca study drug occurs in the course of the study, then the Investigator or other site personnel inform appropriate AstraZeneca representatives immediately, or no later than 24 hours of when he or she becomes aware of it.

The designated AstraZeneca representative works with the Investigator to ensure that all relevant information is provided to the AstraZeneca Patient Safety data entry site. For overdoses associated with a SAE, the standard reporting timelines apply. For other overdoses, reporting must occur within 30 days.

10.1 Adverse Event Characteristics

CTCAE term (AE description) and grade: The descriptions and grading scales found in the revised NCI Common Terminology Criteria for Adverse Events (CTCAE) version 5.0 will be utilized for AE reporting. All appropriate treatment areas should have access to a copy of the CTCAE version 5.0. A copy of the CTCAE version 5.0 can be downloaded from the CTEP web site:

- a. Adverse event monitoring and reporting is a routine part of every clinical trial.
- b. Identify the grade and severity of the event using the CTCAE version 5.0.
- c. Determine whether the event is expected or unexpected (see Section 10.2).
- d. Determine if the adverse event is related to the study intervention (agent, treatment or procedure) (see Section 10.3).
- e. Determine whether the event must be reported as an expedited report. If yes, determine the timeframe/mechanism (see Section 10.4).
- f. Determine if other reporting is required (see Section 10.5).
- g. Note: All AEs reported via expedited mechanisms must also be reported via the routine data reporting mechanisms defined by the protocol (see Sections 10.53 and 18.0).

Each CTCAE term in the current version is a unique representation of a specific event used for medical documentation and scientific analysis and is a single MedDRA Lowest Level Term (LLT).

NOTE: A severe AE, as defined by the above grading scale, is NOT the same as serious AE which is defined in the table in Section 10.4.

10.2 Expected vs. Unexpected Events

Expected events - are those described within the Section 15.0 of the protocol, the study specific consent form, package insert (if applicable), and/or the investigator brochure, (if an investigator brochure is not required, otherwise described in the general investigational plan).

Unexpected adverse events or suspected adverse reactions are those not listed in Section 15.0 of the protocol, the study specific consent form, package insert (if applicable), or in the investigator brochure (or are not listed at the specificity or severity that has been observed); if an investigator brochure is not required or available, is not consistent with the risk information described in the general investigational plan.

Unexpected also refers to adverse events or suspected adverse reactions that are mentioned in the investigator brochure as occurring with a class of drugs but have not been observed with the drug under investigation.

10.3 Assessment of Attribution

When assessing whether an adverse event is related to a medical treatment or procedure, the following attribution categories are utilized:

Definite - The adverse event *is clearly related* to the agent(s).

Probable - The adverse event *is likely related* to the agent(s).

Possible - The adverse event *may be related* to the agent(s).

Unlikely - The adverse event *is doubtfully related* to the agent(s).

Unrelated - The adverse event *is clearly NOT related* to the agent(s).

Events determined to be possibly, probably or definitely attributed to a medical treatment suggest there is evidence to indicate a causal relationship between the drug/device and the adverse event.

10.31 EXPECTED Serious Adverse Events: Protocol Specific Exceptions to Expedited Reporting

For this protocol only, the following Adverse Events/Grades are expected to occur within this population and do not require Expedited Reporting. These events must still be reported via Routine Reporting (see Section 10.53). *

System Organ Class (SOC)	Adverse event/ Symptoms	CTCAE Grade at which the event will not be expeditedly reported.
Gastrointestinal Disorders	Diarrhea	Any Grade
	Dyspepsia	
	Nausea	
	Vomiting	
	Colitis	Grades 1-3
	Pancreatitis	
General disorders and administrations site conditions	Fatigue (asthenia, lethargy, malaise)	Any Grade
Hepatobiliary disorders	Cholecystitis	Grades 1-3
Infections and infestations	Lung Infection	Grades 1-3
	Sinusitis	
	Skin infection	
	Urinary tract infection	
Investigations	Alkaline phosphatase increased	Any Grade
	Alanine aminotransferase increased	
	Aspartate aminotransferase increased	
	Lymphocyte count decreased	
	Weight loss	
Metabolism and nutrition disorders	Anorexia	Any Grade
	Dehydration	
	Hyperkalemia	
	Hypocalcemia	

Musculoskeletal and connective tissue disorders	Hypomagnesemia	Any Grade
	Hyponatremia	
	Arthralgia	
	Back pain	
Skin and subcutaneous tissue disorders	Musculoskeletal and connective tissue disorder – Other (muscle spasms)	Any Grade
	Alopecia	
	Rash acneiform	
	Rash maculo-papular	
	Palmar-plantar erythrodysesthesia syndrome	

These exceptions only apply if the adverse event does not result in hospitalization. If the adverse event results in hospitalization, then the standard expedited adverse events reporting requirements must be followed.

The following hospitalizations are not considered to be SAEs because there is no “adverse event” (i.e., there is no untoward medical occurrence) associated with the hospitalization:

- Hospitalizations for respite care
- Hospitalization planned before informed consent (where the condition requiring the hospitalization has not changed post study drug administration)
- Hospitalization for routine maintenance of a device (e.g., battery replacement) that was in place before study entry

*Report any clinically important increase in the **rate** of a serious suspected adverse reaction (at your study) site over that which is listed in the protocol or investigator brochure as an expedited event.

*Report an expected event that is greater in severity or specificity than expected as an expedited event

*An investigational agent/intervention might exacerbate the expected AEs associated with a commercial agent. Therefore, if an expected AE (for the commercial agent) occurs with a higher degree of severity or specificity, expedited reporting is required.

A list of known/expected AEs is reported in the investigator brochure, package insert or the literature, including AEs resulting from a drug overdose.

10.331 Death

- Any death occurring within 30 days of the last dose, regardless of attribution to an agent/intervention under an IND/IDE requires expedited reporting within 24-hours.
- Any death occurring greater than 30 days with an attribution of possible, probable, or definite to an agent/intervention under an IND/IDE requires expedited reporting within 24-hours.

- **Reportable categories of Death**
 - Death attributable to a CTCAE term.
 - Death Neonatal: A disorder characterized by cessation of life during the first 28 days of life.
 - Death NOS: A cessation of life that cannot be attributed to a CTCAE term associated with Grade 5.
 - Sudden death NOS: A sudden (defined as instant or within one hour of the onset of symptoms) or an unobserved cessation of life that cannot be attributed to a CTCAE term associated with Grade 5.
 - Death due to progressive disease should be reported as **Grade 5 “Disease progression”** under the system organ class (SOC) General Disorders and Administration Site Conditions. Evidence that the death was a manifestation of underlying disease (e.g., radiological changes suggesting tumor growth or progression: clinical deterioration associated with a disease process) should be submitted.

10.332 Secondary Malignancy

- A *secondary malignancy* is a cancer caused by treatment for a previous malignancy (e.g., treatment with investigational agent/intervention, radiation or chemotherapy). A secondary malignancy is not considered a metastasis of the initial neoplasm.
- All secondary malignancies that occur following treatment with an agent under an IND/IDE to be reported. Three options are available to describe the event:
 - Leukemia secondary to oncology chemotherapy (e.g., Acute Myelocytic Leukemia [AML])
 - Myelodysplastic syndrome (MDS)
 - Treatment-related secondary malignancy
- Any malignancy possibly related to cancer treatment (including AML/MDS) should also be reported via the routine reporting mechanisms outlined in each protocol.

10.333 Second Malignancy

- A second malignancy is one unrelated to the treatment of a prior malignancy (and is NOT a metastasis from the initial malignancy). Second malignancies require ONLY routine reporting.

10.334 Pregnancy

Prior to obtaining private information about a pregnant woman and her infant, the investigator must obtain consent from the pregnant woman and the newborn infant's parent or legal guardian before any data collection can occur. A consent form will need to be submitted to the IRB for these subjects if a pregnancy occurs. If informed consent is not obtained, no information may be collected. *In cases of fetal death, miscarriage or abortion the mother is the patient. In cases where the child/fetus experiences a serious adverse event other than fetal death, the child/fetus is the patient.*

All pregnancies and outcomes of pregnancy should be reported to AstraZeneca except for:

- If the pregnancy is discovered before the study patient has received any study drug
- Pregnancies in the partner of male subjects

If a pregnancy is reported, the investigator should inform the sponsor within 24 hours of learning of the pregnancy.

Abnormal pregnancy outcomes (e.g., spontaneous abortion, fetal death, stillbirth, congenital anomalies, and ectopic pregnancy) are considered SAEs.

Maternal exposure

If a patient becomes pregnant during the course of the study, olaparib should be discontinued immediately.

Pregnancy itself is not regarded as an adverse event unless there is a suspicion that the investigational product under study may have interfered with the effectiveness of a contraceptive medication. Congenital abnormalities/birth defects and spontaneous miscarriages should be reported and handled as SAEs. Elective abortions without complications should not be handled as AEs. The outcome of all pregnancies (spontaneous miscarriage, elective termination, ectopic pregnancy, normal birth or congenital abnormality) occurring from the date of the first dose of study medication until 1 month after the last dose of study medication should be followed up and documented even if the patient was discontinued from the study.

If any pregnancy occurs in the course of the study, then the Investigator or other site personnel informs the appropriate AstraZeneca representatives within 1 day i.e., immediately but no later than 24 hours of when he or she becomes aware of it.

The designated AstraZeneca representative works with the Investigator to ensure that all relevant information is provided to the AstraZeneca Patient Safety data entry site within 1 or 5 calendar days for SAEs and within 30 days for all other pregnancies.

The same timelines apply when outcome information is available.

Paternal exposure

Male patients should refrain from fathering a child or donating sperm during the study and for 3 months following the last dose.

Pregnancy of the patient's partners is not considered to be an adverse event. However, the outcome of all pregnancies (spontaneous miscarriage, elective termination, ectopic pregnancy, normal birth or congenital abnormality) occurring from the date of the first dose until 3 months after the last dose should, if possible, be followed up and documented.

10.4 Expedited Adverse Event Reporting Requirements Studies using Commercial Agent(s) ONLY:

10.41 Expedited Reporting via the **MedWatch 3500A Form** for Adverse Events That Occur Within 30 Days¹ of the Last Dose of the Commercial Agent

FDA REPORTING REQUIREMENTS FOR SERIOUS ADVERSE EVENTS (21 CFR Part 312) NOTE: Investigators MUST immediately report to the sponsor ANY Serious Adverse Events, whether or not they are considered related to the investigational agent(s)/intervention (21 CFR 312.64) An adverse event is considered serious if it results in ANY of the following outcomes: 1) Death 2) A life-threatening adverse event 3) An adverse event that results in inpatient hospitalization or prolongation of existing hospitalization for ≥ 24 hours 4) A persistent or significant incapacity or substantial disruption of the ability to conduct normal life functions 5) A congenital anomaly/birth defect. 6) Important Medical Events (IME) that may not result in death, be life threatening, or require hospitalization may be considered serious when, based upon medical judgment, they may jeopardize the patient or subject and may require medical or surgical intervention to prevent one of the outcomes listed in this definition. (FDA, 21 CFR 312.32; ICH E2A and ICH E6).		
ALL SERIOUS adverse events that meet the above criteria MUST be immediately reported to the sponsor within the timeframes detailed in the table below.		
Hospitalization	Grade 1 and Grade 2 Timeframes	Grade 3-5 Timeframes
Resulting in Hospitalization ≥ 24 hrs	7 Calendar Days	24-Hour; 3 Calendar Days
Not resulting in Hospitalization ≥ 24 hrs	Not required	
Expedited AE reporting timelines are defined as: ○ “24-Hour; 3 Calendar Days” - The AE must initially be reported within 24 hours of learning of the AE, followed by a complete expedited report within 3 calendar days of the initial 24-hour report. ○ “7 Calendar Days” - A complete expedited report on the AE must be submitted within 7 calendar days of learning of the AE.		
¹ Serious adverse events that occur more than 30 days after the last administration of investigational agent/intervention and have an attribution of possible, probable, or definite require reporting as follows: Expedited 24-hour notification followed by complete report within 3 calendar days for: 
 All Grade 3, 4, and Grade 5 AEs Expedited 7 calendar day reports for: 
 Grade 2 AEs resulting in hospitalization or prolongation of hospitalization ² For studies using PET or SPECT IND agents, the AE reporting period is limited to 10 radioactive half-lives, rounded UP to the nearest whole day, after the agent/intervention was last administered. Footnote “1” above applies after this reporting period. Effective Date: May 5, 2011		

Special Instructions:

- Follow site-specific reporting guidelines.
- Expedited reports must be submitted to the FDA vis MedWatch 3500A Form found:

- [REDACTED]
- Instructions for completing the MedWatch 3500A:
[REDACTED]
 - Submit copies along with the US ESR SAE Report Coversheet found on the ACCRU Website to the ACCRU SAE Coordinator via email at [REDACTED]
 - The ACCRU SAE Coordinator will forward to the funding sponsor via email at [REDACTED]
 - The ACCRU SAE Coordinator will forward to ACCRU IND Coordinator [REDACTED] as appropriate. The ACCRU IND Coordinator will assist the sponsor-investigator in notifying the FDA if required.

10.5 Other Required Reporting

10.51 Unanticipated Problems Involving Risks to Subjects or Others (UPIRTSOS) in general, include any incident, experience, or outcome that meets **all** of the following criteria:

1. Unexpected (in terms of nature, severity, or frequency) given (a) the research procedures that are described in the protocol-related documents, such as the IRB-approved research protocol and informed consent document; and (b) the characteristics of the subject population being studied;
2. Related or possibly related to participation in the research (in this guidance document, possibly related means there is a reasonable possibility that the incident, experience, or outcome may have been caused by the procedures involved in the research); and
3. Suggests that the research places subjects or others at a greater risk of harm (including physical, psychological, economic, or social harm) than was previously known or recognized.

Some unanticipated problems involve social or economic harm instead of the physical or psychological harm associated with adverse events. In other cases, unanticipated problems place subjects or others at increased *risk* of harm, but no harm occurs.

Note: If there is no language in the protocol indicating that pregnancy is not considered an adverse experience for this trial, and if the consent form does not indicate that subjects should not get pregnant/impregnate others, then any pregnancy in a subject/patient or a male patient's partner (spontaneously reported) which occurs during the study or within 120 days of completing the study should be reported as a UPIRTSO.

If the event meets the criteria for an UPIRTSO, submit to your IRB as required by your institutional policies.

10.52 Baseline and Adverse Events Evaluations

The following pre-treatment symptoms/conditions are to be graded at baseline and adverse events are to be graded at each evaluation using CTCAE v5.0 grading. If CTCAE v5.0 grading is not used, note the grading scale used in the table below:

System Organ Class (SOC)	Adverse event/Symptoms	Baseline	Each evaluation
Gastrointestinal disorders	Diarrhea	# stools per day	X
	Nausea	X	X
	Vomiting	X	X
General Disorders and administration site conditions	Fatigue	X	X
Skin and Subcutaneous Tissue Disorders	Palmar-plantar erythrodysesthesia syndrome	X	X
	Rash maculo-papular	X	X
Vascular disorders	Hypertension	X	X

10.53 **Case Report Forms** - Academic and Community Cancer Research United (ACCRU)

Submit the following AEs not specified in Section 10.5

10.531 Grade 2 AEs deemed *possibly, probably, or definitely* related to the study treatment or procedure.

10.532 Grade 3 and 4 AEs regardless of attribution to the study treatment or procedure.

10.533 Grade 5 AEs (Deaths)

10.5331 Any death within 30 days of the patient's last study treatment or procedure regardless of attribution to the study treatment or procedure requires the submission of an Expedited Adverse Event report (see Section 10.4).

10.5332 Any death more than 30 days after the patient's last study treatment or procedure that is felt to be at least possibly treatment related must also be submitted as a Grade 5 AE, with a CTCAE type and attribution assigned with an Expedited Adverse Event report (see Section 10.4).

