2.2 Secondary

- 2.21 To determine the overall survival of patients with advanced biliary tract cancer with mutations in DNA repair genes treated with olaparib.
- 2.22 To determine the progression free survival of patients with advanced biliary tract cancer with mutations in DNA repair genes treated with olaparib
- 2.23 To determine the objective response of patients with advanced biliary tract cancer with mutations in DNA repair genes treated with olaparib.
- 2.2 To assess the duration of response for patients with advanced biliary tract cancer with mutations in DNA repair genes treated with olaparib who experience an objective response.
- 2.25 To assess the frequency and severity of adverse events in advanced biliary tract cancer patients treated with olaparib.

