Olaparib may modulate the exposure to substrates of OATP1B1 (eg, bosentan, glibenclamide, repaglinide, statins and valsartan), OCT1 (eg, metformin), OCT2 (eg, serum creatinine), OAT3 (furosemide, methotrexate), MATE1 and MATE2K (metformin). In particular, caution should be exercised if olaparib is administered in combination with any statin.

Co-administration of topotecan reduced steady state exposure to olaparib by approximately 20%.

15.17 **Known potential toxicities:**

Very Common potential toxicities (> 10%):

Cardiovascular: Peripheral edema, edema

Central nervous system: Fatigue, headache, dizziness

Dermatologic: Dermatitis, skin rash

Endocrine & metabolic: Hypomagnesemia

Gastrointestinal: Nausea, abdominal pain, vomiting, diarrhea), dysgeusia, dyspepsia, constipation, decreased appetite, stomatitis, upper abdominal pain

Genitourinary: Urinary tract infection

Hematologic & oncologic: Increased MCV, decreased absolute lymphocyte count, anemia, decreased platelet count, neutropenia, leukopenia

Infection: Influenza

Neuromuscular & skeletal: Weakness, musculoskeletal pain, arthralgia, myalgia,

back pain

Renal: Increased serum creatinine

Respiratory: Nasopharyngitis, respiratory tract infection, rhinitis, sinusitis, cough, dyspnea

Miscellaneous: Fever

Common potential toxicities, 1% to 10%:

Cardiovascular: Hypertension, venous thrombosis (embolism)

Central nervous system: Anxiety, depression, insomnia, peripheral neuropathy

Dermatologic: Pruritus, xeroderma (including eczema)

Endocrine & metabolic: Hot flash, hyperglycemia

Genitourinary: Dysuria, urinary incontinence, vulvovaginal disease

Hematologic & oncologic: Myelodysplastic syndrome

Uncommon potential toxicities, <1%: Hypersensitivity reaction, pneumonitis

- 15.18 **Drug procurement:** AstraZeneca will supply the drug to Clinical Research Services, a division of Rx Crossroads by McKesson. Each participating ACCRU treating location will order the drug from Clinical Research Services. Submit the Drug Order Request Form (found on the ACCRU web site) to:

Each participating ACCRU treating location will be responsible for monitoring the supply of olaparib and will use the Drug Order Request Form to order additional supplies as needed.

Outdated or remaining drug is to be destroyed on-site as per procedures in place at each institution.

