16.34 Duration of Response

Duration of response (DoR) is defined for all evaluable patients who have achieved an objective response as the date at which the patient's earliest best objective status is first noted to be either a CR or PR to the earliest date progression is documented, or death if no prior evidence of disease progression. The distribution of DoR will be estimated using the method of Kaplan-Meier. The median DoR and corresponding 95% confidence interval will be reported.

16.354 Adverse Events

All patients who have initiated treatment will be considered evaluable for adverse event analyses. Adverse events by patient will be summarized by frequencies and severity using CTCAE version 5.0. The proportion of patients who experience at least one grade 3+ adverse event (regardless of attribution) will be reported.

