18.1 Submission Timetable

Initial Material(s)

CRF	Active-Monitoring Phase (Compliance with Test Schedule Section 4.0)
Institutional Contacts	≤2 weeks after registration
On-Study	
On-Study: Prior Systemic Therapy ¹	
Adverse Event: Baseline	
RECIST Measurements: Baseline	
Laboratory Tests & Results: Baseline	
Supporting Documentation: Baseline ²	
Concomitant Medications	
Specimen Submission: Blood (Baseline) (see Section 14.0)	
Patient Status: Baseline	
OP and Path Reports (see Section 17.0) ²	
Specimen Submission: Tissue (Baseline) (see Section 17.0)	< 28 days after registration
Off Treatment	Submit ≤2 weeks after registration if withdrawal/refusal occurs prior to beginning protocol therapy
ACCRU Deviation Form ¹	Submit only if applicable during all phases of the study (initial, active and observation)

1. Submit only if applicable.
2. Upload via the Supporting Documentation: Baseline form. This is in addition to the pathology material requirements for tissue submission (Section 17.0). Tumor molecular profiling report demonstrating genetic aberrations that are associated with homologous recombinant repair pathway for eligibility.

Test Schedule Material(s)

CRF	Active-Monitoring Phase (Compliance with Test Schedule Section 4.0)	
	At each evaluation during treatment	At end of treatment
Treatment (Intervention)	X	X
Treatment (Intervention): Dose Modifications, Omissions and Delays ¹	X	
Adverse Events: Solicited	X	X
Adverse Events: Other ¹	X	X
RECIST Measurements ²	X	X
Supporting Documentation ²	X	X
Concomitant Medications	X	
Specimen Submission: Blood (see Section 14.0) ¹		
Specimen Submission: Tissue (see Section		

CRF	Active-Monitoring Phase (Compliance with Test Schedule Section 4.0)	
	At each evaluation during treatment	At end of treatment
17.0) ¹		
Patient Status: Treatment (Intervention)	X	X
Notice of New Primary ¹	X	X
Consent Withdrawal (choose appropriate form) ¹	X	X

 Consent Withdrawal: Specimen Only Consent Withdrawal: All Follow-Up 		
Off Treatment		X
ACCRU Deviation ¹	X	X

1. Submit only if applicable.
2. Upload documentation of response or progression on the Supporting Documentation form.
3. Patients are eligible to be confirmed lost to follow-up after 2_years of unsuccessful contact with the patient.

Follow-up Material(s)

CRF	Event Monitoring Phase¹				
	q. 3 months until PD	At PD	After PD q. 3 mos.	Death	New Primary

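### Grade 1 cytopenias, and grade 2 cytopenias judged unlikely related or unrelated, are not systematically collected, so the planned any-grade summary of olaparib's listed blood toxicities will be incomplete

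*Combined protocol and SAP*

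**What the plan says.** The safety objective (Section 2.2, goal 2.25) is "To assess the frequency and severity of adverse events in advanced biliary tract cancer patients treated with olaparib". The matching analysis in Section 16.354 states "Adverse events by patient will be summarized by frequencies and severity using CTCAE version 5.0", and adds one named proportion: patients with at least one grade 3+ event, whatever the attribution. Neither text sets a lower grade limit.

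Collection works on two tracks.

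- **Solicited events.** Section 10.52 opens with "The following pre-treatment symptoms/conditions are to be graded at baseline and adverse events are to be graded at each evaluation using CTCAE v5.0 grading". The table then lists diarrhea, nausea, vomiting, fatigue, palmar-plantar erythrodysesthesia, maculo-papular rash and hypertension.
- **Other events.** Section 10.53 begins "Submit the following AEs not specified in Section 10.5", which I read as meaning events outside the 10.52 table. It then asks for "Grade 2 AEs deemed *possibly, probably, or definitely* related to the study treatment or procedure", for "Grade 3 and 4 AEs regardless of attribution to the study treatment or procedure", and for deaths.

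Section 15.17 gives the haematological toxicities occurring in more than 10% of patients as "Increased MCV, decreased absolute lymphocyte count, anemia, decreased platelet count, neutropenia, leukopenia". Section 4.0 (footnote 5) has hematology done before each cycle. In Section 18.1 the only laboratory results form is "Laboratory Tests & Results: Baseline"; the table of forms due at each evaluation and at end of treatment has none.

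**The concern.** Cytopenias are prominent among the toxicities this protocol expects, and Section 8.2 devotes its most detailed rules to them, yet they fall on the thresholded track. Two things follow.

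First, a frequency and severity table with no stated floor would show related grade 2 and all grade 3+ cytopenias, with the lower grades present only by accident. A reader could take the total for a complete any-grade incidence and set it beside the solicited gastrointestinal terms, which are graded at every evaluation.

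Second, whether a grade 2 anemia is counted depends on the investigator's causality call. In a single-arm trial there is no comparator to check that call against. Patients may also enter already anemic: Section 3.17 admits hemoglobin from 9.0 g/dL, while Section 8.2 labels values below 10 g/dL as grade 2. Change from baseline is then the informative quantity, and it needs on-treatment grades.

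The numerical stopping rule in Section 16.52 counts only non-hematologic events. Haematological safety is therefore seen through routine adverse event data and the periodic reviews of Section 16.51, which gives gaps in those data more weight.

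**Working it through.** The plan states no figure on this point, so there is none to reproduce. The check is a cross-reading, followed by an illustration of size.

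**1. Terms.** Solicited in 10.52: 7, of which 0 are haematological. Haematological terms above 10% in 15.17: 6. One of these, increased MCV, is not a cytopenia, so 6 − 1 = 5 cytopenias: anemia, neutropenia, leukopenia, decreased platelets and decreased lymphocytes.

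**2. Routes for an unsolicited cytopenia, by grade.**

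| Event | Routine route in 10.53 |
|---|---|
| Grade 1, any attribution | none |
| Grade 2, unlikely or unrelated | none |
| Grade 2, possible, probable or definite | submitted |
| Grade 3 or 4, any attribution | submitted |

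**3. Could the missing grades be derived from laboratory data?** The counts are measured every cycle, but 18.1 schedules no on-treatment laboratory form. Footnote 5 of Section 4.0 sends each coagulation result to the CRF and gives no such instruction for blood counts.

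**4. Side routes that do exist.**
- Section 8.2 allows interruption for low-grade cytopenias and requires the reason for every interruption or reduction in the eCRF.
- Section 10.41 expedites grade 1 and 2 events with hospitalization of 24 hours or more, and Section 10.1 requires expedited events to be reported routinely as well.
- Section 10.31 lists lymphocyte count decreased at any grade and sends it to routine reporting, but by reference to 10.53, which has no entry for grade 1. These two sections need reconciling.

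Each route selects patients by consequence or by term. None gives an incidence.

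**5. Size.** Let p be the true any-grade rate and f the share of affected patients whose only events are of the uncollected kinds. If none of those patients arrives by a side route and all other affected patients are recorded, the recorded rate is p × (1 − f). The documents give neither p nor f; both are assumed. Section 16.354 counts all treated patients, so I use the maximum accrual of 36 from Section 16.22.

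| p | True patients of 36 | f = 25% | f = 50% | f = 75% |
|---|---|---|---|---|
| 40% | 14.4 | 30% (10.8) | 20% (7.2) | 10% (3.6) |
| 20% | 7.2 | 15% (5.4) | 10% (3.6) | 5% (1.8) |

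For example, 0.40 × (1 − 0.25) = 0.30 and 0.40 × (1 − 0.75) = 0.10. Any capture through step 4 makes the shortfall smaller.

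**6. What does not move.** The grade 3+ proportion is fully fed by 10.532 and 10.533. The 16.52 rule is non-hematologic. The primary endpoint is progression-free status at the first scan.

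**The case against.** The strongest defence is that this is a deliberate and ordinary choice: full collection for a short list and a threshold for the rest, for a drug the protocol treats as IND exempt with a well-established safety profile. The only named adverse event proportion is fully covered, and one sentence in 16.354 stating the threshold would make the reporting accurate. That would make the table honest, but it would still leave goal 2.25 without low-grade data on the main blood toxicities, which are already measured every cycle.

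A reader might infer that low-grade cytopenias are never captured. The documents do not support that, because of the side routes in step 4 above.

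A reader might also infer that pre-existing anemia cannot be told from new anemia. That does not follow either: hematology is required within 7 days before registration, a baseline laboratory form is scheduled, and a grade can be derived from the hemoglobin value. The gap is on the treatment side.

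Nor is it certain that no on-treatment counts will be entered. Section 4.0 and Appendix III refer to laboratory CRF entries, for coagulation and liver tests, that have no on-treatment row in 18.1, so that timetable may not be a full inventory. The values in any case remain in source records.

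Finally, 15.17 gives no grades, so it does not show that the uncollected grades are the common ones. This stands, and it is why the size can only be illustrated.

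**Conclusion.** The point holds as a matter of incomplete collection. Followed as written, the plan does not systematically record grade 1 cytopenias or grade 2 cytopenias judged unlikely or unrelated, so the any-grade frequency and severity of five toxicities listed above 10% would be understated in the 16.354 summary by an unknown amount. Under the assumed range of 25% to 75% of affected patients having only such events, a true 40% would be recorded as 30% down to 10%, and a true 20% as 15% down to 5%.

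It would be tempting to conclude that the trial's safety assessment as a whole is unreliable. It is not: the grade 3+ proportion, the stopping rule and the primary endpoint are untouched. This is an inexpensive improvement to a secondary objective, not a flaw in the trial's decision rule.

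**What to change.** Add five rows to the 10.52 table: anemia, neutrophil count decreased, white blood cell decreased, platelet count decreased and lymphocyte count decreased, each graded at baseline and at every evaluation from the blood count already drawn. Alternatively, add a per-cycle laboratory form to 18.1 and derive the CTCAE grades from it. In 16.354, report worst grade and shift from baseline for these terms. Reconcile the any-grade entry for lymphocyte count in 10.31 with the thresholds in 10.53.

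Keep palmar-plantar erythrodysesthesia on the solicited list. It is absent from 15.17, but 10.31 lists it as expected at any grade, and removing it would lose data for no gain.

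Cost: five rows on an existing form, or one new form, plus one shift table. There is no extra visit or blood draw; the downside is slightly more data entry per cycle.
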